#### Statistical Analysis Plan

Data will be analyzed using SPSS Statistics 26.0 for Mac. We will use Pearson's chi-squared ( $\chi 2$ ) and one-way analysis of variance (ANOVA) to compare demographic variables and baseline psychopathological characteristics of the three groups. To represent within-participant dependencies in the models, we will specify an unstructured correlation matrix. We will first apply a full factorial model across the four time points (baseline, post-intervention, 14- and 30-day follow-ups) for treatment-seeking intentions and three time points (baseline, 14- and 30-day follow-ups) for clinical symptoms. Group × time interaction terms will test the intervention effect hypothesis of greater treatment-seeking in the two video groups. If between-group differences are found, post hoc tests will be used to compare each group pair, including the overall changes from baseline assessment to 30-day follow-up. Effect sizes will be reported using Cohen's d when appropriate. All statistical tests will be two-sided, using  $\alpha < 0.05$ .

Protocol Title: Version Date: The COVID-19 and healthcare workers: an 10/20/2020

active intervention

Protocol Number:

8032

Clinic: First Approval:

07/13/2020 **Anxiety Disorders Clinic** 

**Expiration Date:** No Expiration

Contact Principal Investigator: Principal Investigator: [name], PHD

**[name]** Email:

[contact]

Co-Investigator(s): [contact] [name], MPH

> Research Chief: [name]

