#### **Amendment**

Describe the change(s) being made

Currently, we assess participants at pre-intervention, post-intervention, 14-day follow-up and 30-day follow-up. For each step of the study the compensation fee is \$1.10.

We would like to add a 90-day follow-up, and conduct the same assessment as in 30-day follow-up and to add 1 item to inquire if the participant contacted mental health professionals.

In addition, the overall compensation for the study is now \$4.40.

Provide the rationale for the change(s)

We would like to understand longer-term effects of the intervention and if an observed change in help-seeking intentions is translate to change in help-seeking behavior.

Comment on the extent to which the proposed change(s) alter or affect risks/benefits to subjects We assess that there is no affect on risks/benefits to subject.

Comment on if the proposed change(s) require a modification to the Consent Form (CF)

We don't think a change in CF is needed.

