## **Specific Aims and Hypotheses**

Specific Aims and Hypotheses

The overarching goal of this study is to examine the effect of video intervention in reducing stigma and fear, and improving help seeking behavior among health care providers across the US.

In a sizable randomized controlled trial (N=1,200, general population), with pre-, post- and follow-up assessments (day 14, day 30 **and 90 day**), we aim to (1) determine whether video-based intervention reduce stigma and fear, and increase help-seeking behavior in relation to COVID-19 among health care providers, and (2) compare high risk areas (e.g., NY) to low risk areas (e.g., Montana) on intervention outcomes, and (3) test whether symptoms of depression, anxiety, PTSD and Moral Injury, that will be measured by Patient Health Questionnaire (PHQ-9), Generalized Anxiety Disorder (GAD-7), the Primary Care PTSD Screen for DSM-5 (PC-PTSD-5), and the Moral Injury Events Scale (MIES) would change overtime.

Hypotheses: We hypothesize that (1) the brief video intervention will have greater impact in reducing stigma and fear, and in increasing help-seeking behavior in relate to COVID-19 than the control groups in comparison to pre-intervention and to non-video conditions, (2) High risk areas will have increased baseline rates of anxiety, depression and PTSD, and (3) the brief video is expected to have greater impact in reducing symptoms of depression, GAD and PTSD.

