#### **Assessment Instruments**

Create a table or give a brief description of the instruments that will be used for assessment Questions for the pre- and post-intervention (day 1) and follow-ups (day 14, day 30 and **day 90**). Baseline Questionnaire (will be conducted pre intervention only) will include four questions regarding demographics (age, sex, ethnicity and race). Based on previous studies it is estimated the response time will be around 30 seconds.

Three questionnaires will be conducted at pre- and post-intervention (day 1) and follow-up (day 14, day 30 and day 90):

- 1. Attitude towards COVID-19 attitude towards COVID-19 questions were adapted from a measure created by Berger et al. about stigma and fear towards people with HIV. The questionnaire will include six questions and based on previous studies it is estimated the response time for 50 seconds.
- 2. Attitude towards seeking help Attitude towards help seeking will be based on the ATSPPH-SF (Attitudes Towards Seeking Professional Psychological Help Scale), and will include 5 questions (0-disagree, 3-agree). One table will be created to include all 5 questions in one screen. Based on previous studies it is estimated the response time will be around 40 seconds.
- 3. COVID-19 related behaviors and experiences was developed by the researchers and will include six questions regarding social media use, news consumption, social contact, previous contact with a known COVID-19 patient and if the participant has been tested for COVID-19. It is estimated the response time will be around 50 seconds.

Three questionnaires will assess clinical symptoms and will be conducted at pre-intervention (day 1) and follow-up (day 14, day 30, and **day 90**):

- 1. GAD-7 questionnaire will include 7 questions that assess anxiety
- 2. PHQ-9 questionnaire will include 9 questions to assess depression
- 3. Primary Care PTSD screen for DSM-5 will include 5 yes/no questions to assess PTSD. Three tables will be created, one for each questionnaire. Based on previous studies it is estimated the response time will be 150 seconds.

One questionnaire will assess Moral Injury (MIES), and includes 9 items (50 seconds).

In sum, the estimate time for day 1 (pre and post intervention) is 7-9 minutes for intervention groups and 5-7 minutes for control. The estimate time for each follow up is 4-7 minutes (days 14, 30 and 90).

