#### In day 90, we will add the following question:

Over the last three months (you may choose more than one answer):

- 1. I started to take medications to improve my mental condition
- 2. I started psychological treatment

- 3. I contacted professionals (via email/phone/in person) regarding the possibly of starting a psychological treatment
- 4. I am planing to contact professionals regarding the possibility of starting a psychological treatment in the future
- 5. None of the above
- 6. Prefer not to answer

Please attach copies, unless standard instruments are used

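### The planned group × time test to day 30 cannot support a conclusion about treatment-seeking behavior, and the only behavior data (day 90) have no planned analysis

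*Combined protocol and SAP*

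**What the plan says.** The Statistical Analysis Plan states: "We will first apply a full factorial model across the four time points (baseline, post-intervention, 14- and 30-day follow-ups) for treatment-seeking intentions". It continues that the group × time interaction terms are the test of "the intervention effect hypothesis of greater treatment-seeking in the two video groups". It gives no instrument, item list or score for this outcome, and its last time point is day 30.

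Specific Aims and Hypotheses words hypothesis 1 in terms of behavior: "the brief video intervention will have greater impact in reducing stigma and fear, and in increasing help-seeking behavior".

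Under Assessment Instruments, the repeated help-seeking measure is described thus: "Attitude towards help seeking will be based on the ATSPPH-SF". The description adds that it "will include 5 questions (0-disagree, 3-agree"). It is given before and after the intervention on day 1 and at days 14, 30 and 90.

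The Amendment section says the investigators want to learn about longer-term effects and "if an observed change in help-seeking intentions is translate to change in help-seeking behavior". To that end a multiple-response question was added at day 90 only. Options 1-3 are acts: starting medication, starting psychological treatment, and "I contacted professionals (via email/phone/in person) regarding the possibly of starting a psychological treatment". Option 4 is a plan to contact a professional, option 5 is none of these, and option 6 is a refusal to answer.

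**The concern.** Three constructs are in play: attitude to seeking help, intention to seek it, and having sought it. The aims promise the third, the SAP names the second, and the instrument list labels the repeated scale as the first. The amendment treats intention and behavior as different things and adds data to connect them, yet the SAP attaches the treatment-seeking hypothesis to a test that contains none of those data.

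A significant interaction on the repeated scale could therefore be reported as more treatment-seeking, although no one's treatment-seeking entered the analysis. The day-90 answers, which could confirm or contradict that claim, have no pre-specified test. Whether and how they are reported would be decided after the data are seen. The same applies to which items form the repeated score.

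**Working it through.** The SAP states no figure for this point, so there is none to reproduce. The check is to set its outcome against every instrument and its schedule.

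| Measure (Assessment Instruments and day-90 question) | Construct | Times | In the SAP models? |
|---|---|---|---|
| Five items based on the ATSPPH-SF | Labelled attitude; item wording not shown | Pre, post, days 14, 30, 90 | Probably, to day 30; not named |
| COVID-19 behaviors and experiences, six questions | Media and news use, social contact, COVID-19 contact and testing | Same | Not named; no listed topic is treatment-seeking |
| Day-90 question, options 1-3 | Treatment-seeking acts | Day 90 only | No |
| Day-90 question, option 4 | Planned contact (intention) | Day 90 only | No |

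1. Repeated instruments labelled as treatment-seeking intentions: 0. Repeated instruments on help-seeking attitude: 1. Repeated instruments on treatment-seeking behavior: 0. Single-time items on behavior or planned contact: 1, outside the SAP's time points.
2. The SAP's four time points (baseline, post-intervention, days 14 and 30) coincide with the attitude scale's schedule up to day 30. That scale is the likely source of the intentions outcome.
3. Whether its items ask about attitude or intention, they do not record that anyone contacted a professional or started treatment. A group × time effect on them is not evidence of behavior.
4. Options 1-3 are such evidence. They have no baseline value, so they cannot enter a change-from-baseline model, but a randomized comparison of day-90 proportions does not need one.

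**Is a day-90 comparison worth specifying?** This is a feasibility check only. Inputs from the documents: 1,200 participants, three arms, two-sided 0.05. Assumptions: equal arms (400 each, so 800 video v 400 control), 80% power, and control proportions p0 of 5%, 10% and 15%. The detectable p1 solves

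p1 − p0 = 1.96 × √[p̄(1−p̄)(1/n1 + 1/n0)] + 0.842 × √[p1(1−p1)/n1 + p0(1−p0)/n0], where p̄ = (n1·p1 + n0·p0)/(n1 + n0).

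- Full retention, p0 = 0.10, 800 v 400: the solution is p1 = 0.158, with p̄ = 0.139. The right side is 1.96 × 0.0212 + 0.842 × 0.0198 = 0.0415 + 0.0167 = 0.058, or 5.8 points.
- 50% retention, p0 = 0.10, 400 v 200: the solution is p1 = 0.186, with p̄ = 0.157. The right side is 1.96 × 0.0315 + 0.842 × 0.0288 = 0.0618 + 0.0242 = 0.086, or 8.6 points.

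The same formula gives, in percentage points:

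| Assumed control proportion | Full retention (800 v 400) | 50% retention (400 v 200) |
|---|---|---|
| 5% | 4.5 | 6.9 |
| 10% | 5.8 | 8.6 |
| 15% | 6.7 | 9.8 |

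One video arm against control at p0 = 10% needs 6.7 points (400 v 400), or 10.0 at 50% retention (200 v 200).

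**The case against.** The strongest reply is that this is one scale under two labels. The items are only based on the ATSPPH-SF and their wording is not shown. The schedules match to day 30, and the amendment refers to a change in help-seeking intentions as something the existing measures would reveal. On that reading, treatment-seeking in the SAP is shorthand for the intentions named one sentence before.

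Much of this stands. A reader might infer that intention is not measured by any repeated instrument; the documents do not show that, because intention-worded items cannot be ruled out. A reader might also take this to be the trial's main outcome; the SAP names no primary outcome and only models this one first. Nor do the documents say that the five items are summed, so no score range can be asserted. If inconsistent labelling were the whole matter, it would be a request for clarification.

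It can also be said that the day-90 gap is wider than this outcome, since the SAP stops at day 30 for everything it models. That is true, but it matters most here: for the other measures day 90 adds a later time point, whereas for behavior it is the only one.

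Finally, the detectable differences describe the proposed analysis, not the size of the defect, and they rest on assumed rates. That is accepted; the point does not depend on them.

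What the reply does not meet is hypothesis 1. It is stated as behavior, and neither reading of the scale makes it a measure of behavior.

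**Conclusion.** The concern holds in this form: followed exactly, the plan cannot answer its own question about help-seeking behavior. The repeated scale can support a conclusion about attitude, or about intention if its items ask about it. The only behavior data, options 1-3 at day 90, have no planned analysis, although the amendment collects them for that purpose. This rests on comparing the text of the sections cited and on no numerical assumption. It does not establish that intentions go unmeasured.

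The change should be made before the data are analysed. How precisely day 90 can answer the question depends on the control proportion and on retention, and the documents give neither. Under the assumptions above, the detectable rise for pooled video v control runs from 4.5 points (5% control, full retention) to 9.8 points (15% control, 50% retention).

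**What to change.** In the SAP:

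1. Name the five ATSPPH-SF-based items and state how they are scored. Use one term for that outcome throughout, and limit its conclusion to the attitude or intention that the items measure.
2. Add a pre-specified day-90 behavior analysis: any of options 1-3 v none of them, pooled video arms v control, reported as a risk difference with 95% CI.
3. Count respondents who choose only option 4 as showing no behavior, and report option 4 separately as intention.
4. Treat option 6 (refusal) and day-90 dropout as missing. Specify a sensitivity analysis, for example counting all missing as no behavior and then varying the assumed proportion among the missing by arm.

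The cost is SAP text and one extra binary analysis of data the protocol already collects; no new assessment is needed. The headline claim becomes narrower, and the behavior estimate will be only as precise as day-90 retention allows.

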## **Study Procedures**

Describe the procedures required for this study

Participants will be randomly assigned to either a) a 120-second video-based intervention (day 1 and a "booster intervention" of the same content on day 14 of the study) featuring the personal story of a health care provider with COVID-19, his struggles and barriers to care, (b) video-based intervention (day 1 only), and a written description of the same story on day 14 (c) no-intervention control arm (questionnaires only).

Participants of all study arms will be invited to participate in a follow up survey in days 14, 30 and 90. We will invite the participants by using AMT messaging system.

The video content/written vignette: "Martha is a 35-year-old nurse who lives in NYC with her husband (Dave). She works at intensive care unit in a large hospital, and her husband was fired recently from his job as a waiter due to COVID-19. She has never been diagnosed with anxiety, depression or any other mental health issues. Lately, she finds herself experiencing nightmares as well as unexpected fears. She is feeling worried about money, about what might happen if she becomes infected with COVID-19, and about the safety of her parents as well. To Martha it seems that everything has changed since the pandemic began. Recently these worries mean she has had trouble falling asleep, she feels depressed and he feels anxious. Her husband suggested that she could try seeking help. When he first suggested this she dismissed him

saying, "What if people know I went to a psychologist? They might think I'm crazy. Also, what if they suggest I take meds? I don't want to take any... And if my colleges found out they might think I'm weak...". Martha was very resistant to even the idea at first. After a while however, when she realized that how she felt was only getting worse, she agreed to seek professional help. She found a therapist that she now meets with once a week, and since this started, she has reported that she is feeling much better."

You can upload charts or diagrams if any

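### Arms (a) and (b) are treated alike until day 14, but the only pairwise contrast the SAP names is change from the day-1 baseline, which is valid but less precise than the collected data allow

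*Combined protocol and SAP*

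**What the plan says.** The protocol (Study Procedures) gives arm (a) a video on day 1 and a booster "of the same content on day 14 of the study". Arm (b) is described as "b) video-based intervention (day 1 only), and a written description of the same story on day 14". Arm (c) completes questionnaires only. The day-14 survey and the day-14 material fall on the same day, and their order is not stated.

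On measurement, the protocol (Assessment Instruments) states: "Three questionnaires will be conducted at pre- and post-intervention (day 1) and follow-up (day 14, day 30 and day 90". This covers the help-seeking attitude scale. The anxiety, depression and PTSD scales are taken before the intervention and at follow-up, with no immediate post-intervention score.

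The SAP states: "We will first apply a full factorial model across the four time points (baseline, post-intervention, 14- and 30-day follow-ups) for treatment-seeking intentions". The symptom scales are modelled with one visit fewer: "three time points (baseline, 14- and 30-day follow-ups) for clinical symptoms". For dependence within participants, "we will specify an unstructured correlation matrix". If groups differ, "post hoc tests will be used to compare each group pair, including the overall changes from baseline assessment to 30-day follow-up". This is the only pairwise contrast named. The SAP mentions no adjustment for earlier scores and no constraint on the means of arms (a) and (b) before day 14.

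**The concern.** Until the day-14 material is delivered, arms (a) and (b) are one randomised group under one treatment. Their true means are therefore equal at baseline, at post-intervention and, if the survey comes first, at day 14. A full factorial model still estimates separate means for the two arms at each of these visits. The named contrast then subtracts the day-1 baseline difference in full and makes no use of the later pre-booster scores.

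This matters because the day-14 material is the only thing that separates (a) from (b). A null result for this pair could be read as showing that repeating the video adds nothing over a written version. Such a reading depends on how precisely the pair is compared, and better precision is available here without collecting more data.

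**Working it through.** **Inputs.** The total of 1,200 is from the protocol (Description of Subject Population). It has no effect size, SD, power or correlation behind it, so there is no planned figure to reproduce. On error rate, the SAP says "All statistical tests will be two-sided, using" a level of 0.05. The following are assumptions: equal allocation (400 per arm), SD of 1 at each visit, equal correlation r between visits with r = 0.5 to 0.8, and a true (a) v (b) difference of 0.15 SD at day 30.

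**Formulas** (variance per participant, complete data):
- Change from baseline: 2(1 − r).
- Day 30 adjusted for k earlier scores: 1 − k r² / [1 + (k − 1) r].

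| r | Change | Baseline (k = 1) | + post (k = 2) | + day 14 (k = 3) |
|---|---|---|---|---|
| 0.5 | 1.000 | 0.750 | 0.667 | 0.625 |
| 0.6 | 0.800 | 0.640 | 0.550 | 0.509 |
| 0.7 | 0.600 | 0.510 | 0.424 | 0.3875 |
| 0.8 | 0.400 | 0.360 | 0.289 | 0.262 |

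A generalised least squares calculation at r = 0.7 agrees. The full factorial model's baseline-to-day-30 contrast has unit variance 0.600, exactly that of the simple change score. Setting the means of (a) and (b) equal at all three earlier visits gives 0.3875.

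**Standard-error ratios** (square roots of variance ratios, r = 0.5 then r = 0.8):
- Baseline adjustment v change: 0.87, 0.95.
- Baseline + post v change: √(0.667/1.000) = 0.82; √(0.289/0.400) = 0.85.
- Baseline + post v baseline adjustment: √(0.667/0.750) = 0.94; √(0.289/0.360) = 0.90.
- All three v change: √(0.625/1.000) = 0.79; √(0.262/0.400) = 0.81.
- All three v baseline adjustment: √(0.625/0.750) = 0.91; √(0.262/0.360) = 0.85.

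**Power at r = 0.7, 400 per arm.** SE = √(2 × variance / 400); power ≈ Φ(0.15/SE − 1.96).
- Change: SE 0.0548, power 78%.
- Baseline adjustment: SE 0.0505, power 84%.
- Baseline + post: SE 0.0460, power 90%.
- All three: SE 0.0440, power 93%.

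**With 30% missing at day 30** (assumed; missing at random, earlier visits complete). The mixed model now borrows from the earlier scores under every option. Each unit variance rises by the same amount, 0.3875 × (0.3/0.7) = 0.166, to 0.766, 0.676, 0.590 and 0.554. Power is about 68%, 73%, 79% and 81%.

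**Sensitivity to the correlation pattern.** If correlation decays with visit separation (adjacent visits 0.7 to 0.9), the SE ratio against change is 0.76 to 0.80 with baseline + post, and 0.59 to 0.62 with all three.

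**Clinical symptoms.** With no post-intervention score, only baseline is certain. A usable day-14 score would give k = 2, with the same variances as the third column of results.

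**The case against.** The planned contrast is valid. No hypothesis concerns booster video against booster text: the stated one sets the two video groups against no video, and (a) v (b) is one of three pairs tested only if groups differ. The SAP's contrast is introduced by a word that leaves other contrasts open. Every score is in the fitted model and helps when day 30 is missing. Some of the gain is the generic benefit of baseline adjustment and has nothing to do with the booster design. All of this stands, and it sets the priority. It does not remove the point, because the SAP commits to comparing each pair and the improvement needs no new data.

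A reader might infer that the plan throws away about a third of its precision. The documents do not support that as a flat statement. At r = 0.7 the figure is a variance reduction (1 − 0.3875/0.600 = 35%), while the standard error falls by about 20%. It needs the day-14 survey to precede the material, and it rests on assumed correlations. Of the 35%, baseline adjustment alone gives 15% (1 − 0.510/0.600). With 30% missing at day 30, the reduction is 28% (1 − 0.554/0.766). Nor can the three-score figure be applied to symptoms, which have no post-intervention score.

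**Conclusion.** The point holds as one of efficiency, not bias. For (a) v (b), the post-intervention score is a pre-treatment value whatever happens on day 14. The day-14 score is one only if the survey precedes the material.

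For treatment-seeking intentions, the gain certain to be available is baseline plus post-intervention: at equal correlations of 0.5 to 0.8, a standard error 6% to 10% below that of baseline adjustment alone and 15% to 18% below that of the planned contrast. A usable day-14 score widens these to 9% to 15% and 19% to 21%. The power figures also depend on the assumed 0.15 SD difference and equal allocation. For symptoms, the only certain gain is from baseline adjustment.

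It would be wrong to infer that the planned comparison is invalid or that the earlier scores are wholly ignored. Priority: consider.

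**What to change.** For (a) v (b) only, and leaving arm (c) unconstrained:
- **Treatment-seeking intentions:** in the same mixed model, constrain arms (a) and (b) to equal means at baseline and post-intervention, and also at day 14 if that survey precedes the day-14 material. Alternatively, adjust the day-30 score for the same scores. Name the resulting day-30 difference as the estimate for this pair.
- **Clinical symptoms:** constrain baseline, and day 14 only under the same condition.
- **Day-14 order:** state whether the survey comes before or after the material. If after, day 14 is an outcome for this pair and must not be constrained or adjusted for.
- **Comparisons with arm (c):** do not carry the post-intervention or day-14 terms over, since there they follow treatment.

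The cost is a few lines of SAP text and a change of model terms. The assessments are already in the schedule.
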